5.3.2. Estimand

The primary estimand, the main clinical quantity of interest to be estimated in the study, is defined by the following 4 components -

5.3.2.1. Population:

Subjects with high-risk localized or locally advanced prostate cancer who are treatment-naïve and have undergone RP for non-metastatic prostate cancer with post RP PSA ≤ 0.2 ng/mL

5.3.2.2. Variables:

• Time to confirmed BCR (confirmed PSA > 0.2 ng/mL).

5.3.2.3. Intercurrent Events and Strategies:

Table 1

| Intercurrent Events (IE) | Strategy for Addressing IE | Description of Strategy | Data to be Included |
|---|------------------------------------|---|--|
| Treatment discontinuation during treatment phase but continuing in the study. | Treatment Policy strategy | Occurrence of the IE is considered irrelevant in defining the treatment effect of interest | PSA value at the time of the primary analysis |
| Study withdrawal due to any reason, any time during the study (including treatment & study discontinuation during treatment phase) | While-on- Treatment strategy | Response to treatment prior to the occurrence of the IE is of interest | PSA value at the time of study withdrawal |
| Use of restricted and prohibited concomitant therapy any time during the study | While-on- Treatment strategy | Response to treatment prior to the occurrence of the IE is of interest | PSA value at the time of the start of restricted and prohibited concomitant therapy |
| Other protocol deviations | Treatment Policy strategy | Occurrence of the IE is considered irrelevant in defining the treatment effect of interest | PSA value at the time of the primary analysis |
| Death | While-Alive strategy | Response to treatment prior to the occurrence of the IE is of interest | PSA value at the time of death |

5.3.2.4. Population level summary:

Time to confirmed BCR endpoint: Kaplan-Meier method will be used to estimate BCR-free rate at primary time point (24 months) along with 95% confidence interval.

5.3.3. Analysis Methods

The analysis of time to BCR will be performed at the end of study which is defined as the date of last participant's enrolment + 24 months or discontinuation of all study participants from the study, whichever occurs first. The distribution of time to BCR will be estimated using the Kaplan-Meier (KM) method. Median BCR-free time along with 90% confidence interval will be reported with Kaplan-Meier curve. The null hypothesis will be rejected if lower limit of the 90% confidence interval of KM estimate of BCR-free rate at 24 months is > 76%.

Time to unconfirmed BCR will be evaluated using same methodology as sensitivity analysis.

Modified ITT analysis set will be used for the analysis. Subjects with no evidence of BCR will be censored based on following rule:

- If the subject does not have baseline PSA measurement, the subject will be censored on the date of enrollment (Study Day 1)
- If the subject does not have confirmed PSA >= 0.2 ng/mL, the subject will be censored on the date of the last PSA measurement
- If the subject receives a protocol specified prohibited or restricted therapy, PSA measurements on or after such therapy will not be included in the analysis

These censoring rules will be applied appropriately to all intercurrent events in the trial as defined in Table 1. The details are as specified in Table 2.

| Intercurrent Event (IE) / EOS | Censoring (if no event, before the IE) | Assumption |
|--|---|---|
| IE: Study withdrawal due to any reason, any time during the study | PSA value censored at study withdrawal | Non-informative censoring as per censoring rule |
| IE: Use of restricted and prohibited concomitant therapy any time during the study | PSA value censored at the last PSA assessment prior to the time of the start of restricted and prohibited concomitant therapy | Non-informative censoring as per censoring rule |

Table 2: Censoring Rules to be used for intercurrent events

| IE: Death | PSA value censored at the last PSA assessment prior to the time of death | Non-informative censoring as per censoring rule |
|--------------|--|---|
| End of study | (Administratively) censored at the last PSA assessment prior to the end of the study | Non-informative censoring as per censoring rule |

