4.2.2. Study-Specific Ethical Design Considerations

Potential participants will be fully informed of the risks and requirements of the study and, during the study, participants will be given any new information that may affect their decision to continue participation. They will be told that their consent to participate in the study is voluntary and may be withdrawn at any time with no reason given and without penalty or loss of benefits to which they would otherwise be entitled. Only participants who are fully able to understand the risks, benefits, and potential AEs of the study, and provide their consent voluntarily will be enrolled.

While participants have selected RP independent from this study, the primary ethical concern is that adjuvant therapy with apalutamide following RP is not currently standard of care. The cure rate for patients with high-risk localized prostate cancer is approximately 25%. Apalutamide has been proved to significantly delay metastases and improve overall survival, and has a manageable safety profile.²⁵ Participants may discontinue from the study if there are signs of disease progression and then be eligible for other forms of treatment including radiation.

An additional ethical concern is germline and other genetic testing which may warrant counselling. This information and potential interventions may affect not only the participant, but his family. Genetic counselling will be made available through the genetic testing facility.

The total blood volume to be collected is considered to be an acceptable amount of blood to be collected over this time period from the population in this study based upon the standard of the American Red Cross.¹

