10.6. Appendix 6: Prohibited Concomitant Medications

Apalutamide

Drugs known to lower the seizure threshold or cause seizures are prohibited and a representative list is included below:

- Aminophylline/theophylline
- Atypical antipsychotics (eg, clozapine, olanzapine, risperidone, ziprasidone)
- Bupropion
- Lithium
- Meperidine (pethidine)
- Phenothiazine antipsychotics (eg, chlorpromazine, mesoridazine, thioridazine)
- Tricyclic antidepressants (eg, amitriptyline, desipramine, doxepin, imipramine, maprotiline, mirtazapine)

Other prohibited therapies include the following:

- Investigational agents
- Any other prior or current treatment for prostate cancer which includes but not limited to
 - Abiraterone acetate or other CYP17 inhibitors
 - Other hormonal agents for the treatment of prostate cancer
 - Other antineoplastic agents
 - Radiation therapy
 - $5-\alpha$ -reductase inhibitors
 - Chemotherapy
 - Immunotherapy or vaccine therapy for cancer treatment
 - Other anti-androgens (eg, bicalutamide, nilutamide, flutamide, cyproterone acetate, enzalutamide)
 - Bisphosphonates or denosumab unless for management of osteoporosis
 - Systemic ketoconazole (or other azole drugs such as fluconazole or itraconazole)
 - Diethylstilbestrol (DES) or similar
 - Other preparations such as pomegranates or pomegranate juice or saw palmetto, which are thought to have endocrine effects on prostate cancer
 - Radiopharmaceuticals such as strontium (⁸⁹Sr) or samarium (¹⁵³Sm) or similar analogs such as radium-223 (²²³Ra)
 - Spironolactone

If the permissibility of a specific drug/treatment is in question, please contact the sponsor.

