5.3.1. Definition of Endpoint(s)

Time to confirmed BCR will be defined as the time between the date of the first dose of study drug (apalutamide) and the date of the first occurrence of confirmed PSA > 0.2 ng/mL. Confirmation of PSA value will be done within 3-4 weeks regardless of study visit and timing. Depending on timing, this may be captured as an unscheduled visit.

Subjects without confirmed PSA > 0.2 ng/mL (including subjects who are lost-to-follow up) will be censored on their last PSA date during treatment phase of the study. Additional censoring rules are provided in 5.3.3.

The time to unconfirmed BCR (from the first dose of the study drug to the first occurrence of PSA > 0.2 ng/mL) will be used for sensitivity analysis of the primary endpoint using similar methodology.

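### SAP 5.3.3 ends PSA follow-up at any prohibited or restricted therapy: prostate-cancer treatment begun before confirmed BCR is censored as non-informative, and drugs with no stated link to PSA also cost data.

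*SAP*

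**What the plan says.** The third censoring bullet in SAP 5.3.3 reads: "If the subject receives a protocol specified prohibited or restricted therapy, PSA measurements on or after such therapy will not be included in the analysis". Table 1 (SAP 5.3.2.3) names the intercurrent event as "Use of restricted and prohibited concomitant therapy any time during the study" and gives it a while-on-treatment strategy. Table 2 censors the man at his last PSA before the therapy starts, with the assumption "Non-informative censoring as per censoring rule". The row for leaving the study reads "PSA value censored at study withdrawal" and carries the same assumption. A BCR confirmed before the therapy still counts.

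The prohibited list is Protocol Appendix 6. It covers radiation, chemotherapy and "Other hormonal agents for the treatment of prostate cancer". It also says: "Drugs known to lower the seizure threshold or cause seizures are prohibited and a representative list is included below"; that list includes bupropion and lithium. The SAP does not define *restricted*. Protocol Appendix 7 mixes drugs allowed with caution, such as P-gp substrates, with long-term systemic corticosteroids, which are not allowed (up to 4 weeks including taper is).

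Protocol 9.4.2 has no such exclusion, and SAP Appendix 2 records no change from the protocol. The only planned sensitivity analysis of the primary endpoint uses unconfirmed BCR (SAP 5.3.1 and 5.3.3).

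**The concern.** One rule treats salvage radiation and a new antidepressant alike.

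**Prostate-cancer therapy.** Starting it can itself be a sign of suspected recurrence, so non-informative censoring is doubtful for these men. The unconfirmed-BCR analysis recovers a man with a recorded PSA above 0.2 before therapy, but not a man treated before any such value. Withdrawal is a second route. Protocol 4.2.2 says: "Participants may discontinue from the study if there are signs of disease progression and then be eligible for other forms of treatment including radiation". No planned analysis tests the assumption for these men, and the trial is judged by a single-arm comparison with a fixed 76%.

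**Other listed drugs.** A man who starts one during treatment loses his later PSAs, although nothing in the documents links the drug to PSA. Because *restricted* is undefined, two programmers could build different primary datasets from the same text.

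**Working it through.** **Inputs.** n = 94, null 76%, alternative 86%, one-sided 0.05 (Protocol 9.2, SAP 3). Success means that the lower 90% Kaplan-Meier limit exceeds 76% (SAP 5.3.3). The interval scale is not named, so log-log and plain are both shown. How often men start listed therapies is not given, so all shares below are assumptions.

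**The plan's own figure.** On the arcsine scale, n = [(1.645 + 0.842) / (2 × (asin√0.86 − asin√0.76))]² = [2.486 / (2 × 0.1285)]² = 93.6, which rounds up to the stated 94.

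**Cut-offs, everyone followed to 24 months.** S = k/94 and SE = √(S(1−S)/94). The plain limit is S − 1.645·SE. The log-log limit is S raised to the power exp(1.645·SE/(S·|ln S|)). For k = 78, S = 0.8298 and SE = 0.0388.

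| Event-free | Events | Log-log limit | Plain limit |
|---|---|---|---|
| 77 | 17 | 0.743 | 0.754 |
| 78 | 16 | 0.755 | 0.766 |
| 79 | 15 | 0.766 | 0.778 |

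Success needs at most 15 events (log-log) or 16 (plain).

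**Recurring men censored instead of counted.** Recurrences are evenly spaced over months 3 to 23.5, the censored ones are spread over follow-up, and the variance is Greenwood's.

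| Recurrences | Censored | KM | Log-log / plain limit |
|---|---|---|---|
| 16 | 0 | 83.0% | 75.5% / 76.6% |
| 16 | 1 | 84.0% | 76.5% / 77.7% |
| 17 | 0 | 81.9% | 74.3% / 75.4% |
| 17 | 1 | 82.9% | 75.3% / 76.5% |
| 17 | 2 | 83.9% | 76.4% / 77.6% |
| 18 | 2 | 82.8% | 75.2% / 76.3% |
| 18 | 3 | 83.8% | 76.2% / 77.4% |

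Each such man adds about 1 point. With 23 recurrences (about the null, 0.24 × 94 = 22.6), at least seven must be censored.

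**Men who would not have recurred, censored at month 6.** With 15 events, KM is 84.0% with none censored, 83.9% with one and 83.6% with three. With 16 events, three such men move the plain limit from 76.6% to 75.97%, a pass to a fail. So the direction depends on why therapy started.

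**Illustration only.** Suppose the true rate is 76%, a share f of recurrences is censored just before confirmation, and the benchmark cohort counted such men as recurrences. The counted hazard is then (1−f) times the true one, and KM tends to 0.76^(1−f). The pass probability is the binomial chance of at least 79 (log-log) or 78 (plain) event-free men.

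| f | KM limit | Log-log / plain |
|---|---|---|
| 0 | 76.0% | 4.0% / 6.8% |
| 5% | 77.1% | 6.4% / 10.4% |
| 10% | 78.1% | 10.0% / 15.4% |
| 20% | 80.3% | 21.9% / 30.6% |

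**Unrelated drugs.** The true rate is 86% and starts are uniform over 24 months (20,000 simulated trials). Log-log/plain power is 76.2%/84.0% with none affected, 73.9%/82.2% at 10%, 71.9%/80.2% at 20% and 68.8%/78.4% at 30%. A separate simulation with constant-hazard starts kept the mean KM at 86%, so there is no bias when use is unrelated to recurrence.

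**Which drugs, and when.** Exclusion criterion 3 bars men with a chronic need for prohibited drugs, so for those drugs the issue is new starts. Read broadly, *restricted* catches permitted Appendix 7 drugs. Read narrowly, it still catches systemic steroids beyond 4 weeks, which the Appendix 9 rash plan foresees when it asks sites to contact the sponsor if total use will exceed 28 days. On period, Tables 1 and 2 cover the whole study. SAP 6.4 ties prohibited medication to the treatment period, SAP 6.5 defines concomitant medication by the Treatment Phase and places later cancer therapy in its own summary, and Protocol Appendix 7 refers to drugs prohibited on active treatment. These passages must be reconciled.

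**The case against.** The route for cancer therapy is narrow. A PSA above 0.2 is to be confirmed within 3-4 weeks, at an unscheduled visit if necessary, so therapy must start inside that window or before any such value. The main-study schedule lists no imaging; PSA is its only scheduled recurrence measure. Protocol 7.2 does not list progression as a reason for withdrawal, and Protocol 7.1 continues assessments after treatment stops. SAP 6.5 already summarises later cancer therapies. Table 1 chose its strategy openly, so preferring another is partly a choice of estimand. All of this stands, and it limits the likely size. It does not supply an analysis that tests the assumption.

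Four stronger readings are tempting, and the documents do not support them:

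- A reader might infer that the rule can only raise the Kaplan-Meier estimate. It cannot be said: Protocol 2.1 notes evidence for adjuvant radiation, so therapy can begin without recurrence, and censoring such a man lowers the estimate. Nor is the rule clearly laxer than Protocol 9.4.2, which would keep PSAs taken under radiation.
- A reader might infer that the censored man counts as BCR-free at 24 months. He does not; Kaplan-Meier gives him the risk of the men remaining.
- A reader might take the pass probabilities as the trial's error rate. They rest on assumed shares and on an assumption about the benchmark, and the documents give neither.
- A reader might infer that a non-cancer drug started in follow-up certainly ends PSA follow-up. That is contested between the passages above.

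The steroid example is also limited: the rash plan names 20 days of oral steroid plus a taper and does not direct a course beyond 28 days.

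**Conclusion.** The point holds as a should-fix matter, with medium confidence. The exclusion is wider than its purpose needs, and the non-informative assumption is untested for men treated before any PSA above 0.2 or after leaving at signs of progression. If those starts reflect suspected recurrence, the BCR-free rate is biased upward by about 1 point per man compared with counting them as recurrences. If not, it is slightly lowered. The net bias against 76% is unknown, because neither the frequency of such starts nor the benchmark cohort's handling of salvage therapy is stated. The decision is affected only near 16 or 17 recurrences, or 18 with two or three men censored.

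For unrelated drugs the loss is clear during treatment and unsettled in follow-up. It is about 2 power points if 10% of men are affected over 24 months, an assumed share.

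**What to change.** **(a) Narrow the rule.** Limit the SAP 5.3.3 bullet and the matching rows of Tables 1 and 2 to a named list of therapies that treat prostate cancer or alter PSA. Start from the Appendix 6 sub-list of other prostate-cancer treatments, with clinical input on which entries affect PSA. Keep PSAs under treatment policy, as Table 1 already does for other protocol deviations, for all other prohibited or restricted drugs. State whether a systemic steroid course, including one given for rash, is on the list. State the period covered, and reconcile it with SAP 6.4 and 6.5 and Protocol Appendix 7.

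**(b) Add one sensitivity analysis.** Keep the primary endpoint. Pre-specify a repeat of the 24-month decision that counts the start of radiation or non-study systemic prostate-cancer therapy before confirmed BCR as an event on its start date. Use the subsequent-therapy data already collected (Protocol 7.1, SAP 6.5). Label it a conservative bound, and report how many withdrawn men have unknown later treatment. The Table 2 assumption can then stay as one that this analysis tests.

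**Cost.** SAP wording and one extra analysis. Capture may be incomplete: concomitant therapy is recorded to the last study visit (Protocol 6.8) and treatment after progression only where known. The sensitivity estimate may be less favourable. If 1% or 2% of otherwise event-free men (about 1 or 2 of 81) start such therapy without recurrence, the rate it estimates at a true 86% is 0.86 × 0.99 = 85.1% or 0.86 × 0.98 = 84.3%. Its pass probability then falls from 76%/84% (log-log/plain) to 68%/77% or 59%/70%.

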5.4. Secondary Endpoint(s) Analysis

- BCR-free rate at 12 months
- Testosterone recovery rate at 18 and 24 months. Serum testosterone ≥150 ng/dL is defined as testosterone recovery.

5.4.1. Analysis Methods

Analyses of secondary efficacy endpoints will be performed using the methods similar to those for the primary endpoint using modified intent-to-treat analysis set.

Time to testosterone recovery will be analyzed using Kaplan-Meier (KM) method. Quartiles of the distribution along with 95% CI will be estimated. Estimates of testosterone recovery rates at 13-, 18-, and 24-month together with 95% CI will be estimated. Primary analysis censoring rule (5.3.3) as it relates to testosterone, will be used for these analyses.

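### Kaplan-Meier censoring of death and hormonal re-treatment makes the testosterone recovery rate a hypothetical figure, at or above the proportion of men who actually recover

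*SAP*

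**What the plan says.** The secondary endpoint is the testosterone recovery rate at 18 and 24 months. SAP 5.4 sets the threshold: "Serum testosterone ≥150 ng/dL is defined as testosterone recovery". SAP 5.4.1 gives the method: "Time to testosterone recovery will be analyzed using Kaplan-Meier (KM) method", and "Estimates of testosterone recovery rates at 13-, 18-, and 24-month together with 95% CI will be estimated". Protocol 9.4.3 also specifies Kaplan-Meier.

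For censoring, SAP 5.4.1 points back to the primary analysis: "Primary analysis censoring rule (5.3.3) as it relates to testosterone, will be used for these analyses". In Table 2 of SAP 5.3.3 the row for prohibited or restricted therapy reads "PSA value censored at the last PSA assessment prior to the time of the start of restricted and prohibited concomitant therapy", and it applies whenever in the study the therapy starts. The row for death reads "PSA value censored at the last PSA assessment prior to the time of death". The assumption given for both is "Non-informative censoring as per censoring rule".

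Protocol Appendix 6 puts "Other hormonal agents for the treatment of prostate cancer" on the prohibited list. It does not name a restart of GnRH therapy after the planned 12 months.

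Table 1 in SAP 5.3.2.3 declares a while-alive strategy for death and a while-on-treatment strategy for prohibited therapy and for study withdrawal. In each case the interest lies in the response before the event. No hypothetical strategy is declared. No competing-risk or sensitivity analysis is planned for recovery.

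**The concern.** A man who dies before recovery cannot recover, and renewed castration suppresses testosterone by design. Both are competing events for recovery. If they are treated as ordinary censoring, the man leaves the risk set and Kaplan-Meier lets the men who remain stand in for him. The result is a recovery rate for a setting in which nobody dies or is re-treated first, but it would be reported as the recovery rate of the treated men.

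Recovery is likely to be read as a measure of the cost of a year of castration. If such events precede recovery, the planned figure makes that cost look smaller than it was in these men.

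**Working it through.** **Inputs.** The documents give no expected recovery, restart, death or dropout rate, so there is no plan figure for recovery to reproduce. The one stated size is the primary endpoint's sample size. The arcsine formula reproduces it: n = [(1.645 + 0.842) / (2(asin√0.86 − asin√0.76))]² = 93.6, rounded up to 94. Here 94 serves only as a denominator. The testosterone visits used are Months 13, 14, 18 and 24 (Protocol 1.3). With a 3-month depot the last dose is at Month 10, so recovery falls mainly at these visits.

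**Formulas.** Let d be the recoveries at a visit and n the men still at risk just before it.
- 1-KM = 1 − Π(1 − d/n), where men who die or restart are simply removed from n.
- Cumulative incidence = Σ S × d/n, where S is the probability of having had neither recovery nor a competing event up to then. With no other censoring this is recoveries divided by all men.

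The first is never below the second. It is above it whenever a death or restart comes before recovery and recoveries are seen afterwards.

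**Worked example (assumed counts, no other censoring).** N = 94, with 3, 6, 29 and 27 recoveries at the four visits, 65 in all.

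Five competing events: 0, 0, 2 and 3 in the intervals before the four visits.
- After Month 14, 85 of 94 are unrecovered. Two leave, so 83 are at risk at Month 18 and 54 remain after 29 recoveries. Three leave, so 51 are at risk at Month 24 and 24 remain after 27 recoveries.
- Month 18: 1-KM = 1 − (85/94)(54/83) = 41.2%. Proportion recovered = 38/94 = 40.4%.
- Month 24: 1-KM = 1 − (85/94)(54/83)(24/51) = 72.3%. Proportion recovered = 65/94 = 69.1%. The excess is 3.2 points.

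Nine competing events: 1, 0, 3 and 5.
- Month 18: 1-KM = 1 − (84/93)(52/81) = 42.0%, against 40.4%.
- Month 24: 1-KM = 1 − (84/93)(52/81)(20/47) = 75.3%, against 69.1%. The excess is 6.2 points.

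With no competing events the two estimates are equal.

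**Range at Month 24.** Assumptions: 1-KM between 50% and 90%; recoveries split 5/10/45/40% over the four visits; competing events at a constant hazard from Month 12 among men not yet recovered. The table gives 1-KM minus cumulative incidence, in points.

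| Men with an event before recovery | 1-KM 50% | 1-KM 70% | 1-KM 90% |
|---|---|---|---|
| 2% | 0.8 | 1.2 | 1.7 |
| 5% | 2.0 | 3.0 | 4.3 |
| 10% | 4.0 | 6.0 | 8.6 |
| 14% | 5.6 | 8.5 | 12.0 |

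The 14% row is an upper illustration. It is 1 − 0.86, every biochemical recurrence (BCR) expected by 24 months under the design alternative, with each one leading to a restart before recovery.

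**The case against.** **The censoring of restarts is inferred.** Protocol Section 2 defines study intervention as apalutamide plus ADT, so it is unclear whether a GnRH restart is an other hormonal agent. SAP Appendix 5 (6.5) separates concomitant medication, started by the End-of-Treatment visit, from later prostate cancer therapy, and most restarts would fall in the second class. If restarts were not censored, these men would stay in the risk set as unrecovered and that part of the excess would vanish. This ambiguity stands. Against it, Table 2 sets no time limit, and the rule in the SAP 5.3.3 text refers to therapy without the word concomitant. Death is censored on any reading.

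**Recovery absent re-treatment is a legitimate question.** A man re-castrated for recurrence has low testosterone from a second course, not the first. This is a fair reason to keep the Kaplan-Meier figure. It does not make that figure the declared one, because Table 1 sets no hypothetical strategy.

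**The size is assumed, and timing matters.** Only events before recovery count. In a simulation with 70% recovering by Month 24 and 7% of men scheduled to restart, the excess is 3.7 points with restarts over Months 13-20 and 2.0 points with restarts over Months 18-24. The Protocol also names radiation as later treatment (2.2, 4.2.2, 7.1), and a man given radiation alone can still recover.

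**The consequence is small.** At 70% recovered among 94 men, the 95% half-width is 1.96√(0.7 × 0.3/94) = 9.3 points, and no test depends on this endpoint. Both points stand. They limit the importance of the issue, but a wider interval does not correct a figure that answers a different question.

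**Conclusion.** The point holds as a mismatch between estimator and estimand on an untested secondary endpoint. 1-KM is at or above the proportion recovered. On the assumed rates the excess at 24 months is about 1-4 points if 2-5% of men have an event before recovery, about 4-9 points if 10% do, and zero if none do. The primary conclusion is unaffected.

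The documents do not support three stronger readings that a reader might infer:
- *That men who cannot recover are assumed to recover.* Kaplan-Meier gives them the hazard of men still at risk, not certain recovery.
- *That the reported rate will be too high in every sense.* The ordering is relative to the proportion recorded as recovered, and there is an excess only if such events occur before later recoveries. Against true recovery times, widely spaced visits delay detection and push the other way, so the net error is unknown.
- *That the overstatement is 10 points or more.* On the table's assumptions that needs about 14% of men with an event before recovery together with a very high recovery rate. A scenario with 20% restarting exceeds the whole 14% BCR implied by the 86% alternative.

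**What to change.** In SAP 5.4.1, report the 18- and 24-month recovery rates as Aalen-Johansen cumulative incidence with 95% CI. Take as competing events death and start of testosterone-lowering therapy before recovery, including any orchiectomy that occurs despite the prohibition in Protocol 5.3. Write the testosterone rule out in full instead of referring to 5.3.3. It should say that therapy started after the Treatment Phase is covered and that radiation alone is not a competing event. Keep the Kaplan-Meier estimate as a supplementary figure labelled *absent re-treatment*.

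The cost is SAP wording and standard software. Much of the information is already planned: SAP Appendix 5 summarises subsequent prostate cancer therapies, and Protocol 7.1 records treatment after discontinuation for progression, if known. The downside is that the headline recovery rate may be slightly lower.
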